7.1.3. Randomization

Compliance with inclusion/exclusion criteria will be finally verified vs demographic, laboratory test results and clinical information.

Patients fulfilling **all** the inclusion criteria and **none** of the exclusion criteria will be randomized (randomization number assigned) by an Investigator (or designee), randomization to occur within 100 days from the 1st insulin administration.

Randomization is defined as **Study Day 0** with reference to day when IMP administration is started which is defined as **Study Day 1**.

Patients who do not meet the Inclusion Criteria or meet Exclusion Criteria will be considered screen failures (screen failure number assigned) and will not be allowed to be re-considered for inclusion into the study.

7.2. PRE-DOSE ASSESSMENTS & DRUG ADMINISTRATION

7.2.1. Pre-dose assessment - 1st treatment cycle

Assessment to be done before the 1st dose are part of screening evaluation and reported in [Section 7.1.1](#) above. On the day of randomization (Study Day 0), patient will be provided with the Treatment Box - Cycle No. 1 matching his/her randomization number, together with the Diary Card.

Before box delivery, the removable label on the Treatment Box (see [Section 6.4](#)) will be detached and attached to the relevant CRF page.

It is the responsibility of the Investigator (or designee) to explain, and make sure patient fully understands any appropriate treatment related information. This includes, but is not limited to treatment schedule, time of administration, time interval from meals, recording of administration in the Diary Card, etc.

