In order to optimize insulin titration, telephone calls (outside scheduled visits) will be scheduled on a regular basis to ensure timely evaluation of metabolic control and adjustment of insulin regimen. Patients will report their self-monitored glucose levels (logs, glucose meter, etc.) as per site standard diabetes management, but at least weekly up to week 13 \pm 1 and in the 2 weeks before each follow-up visit.

Screening includes evaluation of past medical history and disease-specific clinical information, including date of first insulin administration, and blood sampling for measurement (centralized laboratory) of auto-antibody (anti-GAD; IAA, if obtained within 10 days of the onset of insulin therapy; IA-2 antibody; ZnT8) to confirm T1D diagnosis (**time frame**: from enrolment to randomization).

The following baseline assessments (**time frame**: within 3 weeks before randomization – *consider time for centralized assay of MMTT C-peptide*) will be also performed during the screening period:

- Measurement of blood pressure, heart rate, body weight, height;
- Blood sampling(s) for measurement (local laboratories) of “Safety Laboratory Tests” i.e.: hematocrit, hemoglobin, red blood cells, platelets, white blood cells, differential white blood cells count, sodium, potassium, serum creatinine, serum albumin, blood urea nitrogen, total bilirubin, ALT, AST;
- Evaluation of renal and hepatic function (to be derived from the safety laboratory test results).
- Screening 12 lead ECG, performed using local equipment that allows automatic calculation of the QTcF.
- Pregnancy test (urine dipstick or blood sample), if appropriate;
- Baseline insulin requirement (IU/kg/day averaged over the previous 3 days);
- Blood sampling for measurement (centralized laboratory) of baseline auto-antibody (anti-GAD; IAA; IA-2 antibody; ZnT8 – not to be repeated if “diagnostic” test is done within this timeframe), HbA1c and miR-375 (and T-cell response *ex vivo* at selected sites only).
- Baseline MMTT. Blood samples for measurement (centralized laboratory) of C-peptide, glucose and glucagon will be drawn pre-meal (2 basal samples in the range between -20 to 0) and 15, 30, 60, 90, 120, 180 min after the meal.

Patients fulfilling **all** the inclusion criteria and **none** of the exclusion criteria will be randomized, randomization day being defined as **Study Day 0** with reference to day when IMP administration is started which is defined as **Study Day 1**.

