7.1.2. Screening

Screening, including confirmation of T1D diagnosis, will be performed in enrolled patients.

Screening includes the following assessments, and may be performed in one or more visits, as per details below:

- ✓ **time frame:** from enrolment to randomization (clinical information)
 - Past medical history and disease-specific clinical information, including date of first insulin administration;
 - Blood sampling for measurement (centralized laboratory) of auto-antibody (anti-GAD; IAA, if obtained within 10 days of the onset of insulin therapy; IA-2 antibody; ZnT8) to confirm T1D diagnosis; Samples will be obtained and stored as detailed in [Appendix 14.4.1](#).
- ✓ **time frame:** within 3 weeks before randomization (baseline measurements - *consider time for centralized assay of MMTT C-peptide – results available within 5 working days*)
 - Measurement of blood pressure, heart rate, body weight, height;
 - Blood sampling(s) for measurement (local laboratories) of “Safety Laboratory Tests” i.e.: hematocrit, hemoglobin, red blood cells, platelets, white blood cells, differential white blood cells count, sodium, potassium, serum creatinine, serum albumin, blood urea nitrogen, total bilirubin, ALT, AST;
 - Evaluation of renal and hepatic function (to be derived from the safety laboratory test results).
Renal function will be evaluated by Cl_{cr}, calculated according to the following formula [[Cockcroft-](#)

Gault, 1976]:

$$\text{Male: CLcr} = \frac{[140 - \text{age (years)}] \times \text{Weight (kg)}}{\text{Serum Creatinine } (\mu\text{mol / L)} \times 0.815}$$

$$\text{Female: CLcr} = \frac{[140 - \text{age (years)}] \times \text{Weight (kg)}}{\text{Serum Creatinine } (\mu\text{mol / L)} \times 0.815} \times 0.85$$

Hepatic function will be evaluated by bilirubin and transaminases (ALT and AST).

- Screening 12 lead ECG, performed using local equipment that allows automatic calculation of the QTcF.
- Pregnancy test (urine dipstick or blood sample), if appropriate;
- Baseline insulin requirement (IU/kg/day averaged over the previous 3days);
- Blood sampling for measurement (centralized laboratory) of baseline auto-antibody (anti-GAD; IAA; IA-2 antibody; ZnT8 – not to be repeated if “diagnostic” test is done within this timeframe), HbA1c and miR-375 (and T-cell response *ex vivo* at selected sites only). Sample handling is detailed in [Appendix 14.4.1](#);

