7.2.2. Pre-dose assessment - 2nd and 3rd treatment cycle

Patient will refer to the site within 1 week before the expected date when the 2nd or 3rd treatment cycle is due to start. The following will be evaluated:

- General clinical evaluation to ensure patients has not developed concurrent clinical conditions, including pregnancy in female participants, which in the opinion of the Investigator may pose a safety risk for continuing participation in the study
- Blood sampling(s) for measurement (local laboratories), of serum creatinine, serum albumin, total bilirubin, ALT, AST. Renal and hepatic function will be evaluated as per details in [Section 7.1.1](#) above.
- 12 lead ECG performed using local equipment that allows automatic calculation of the QTcF. If the QTcF is EITHER > 500 msec OR has increased by > 60 msec from baseline value, a second reading will be obtained 1 hour later.
- Pregnancy test (urine dipstick or blood sample), if appropriate.
- **On pre-dose 2nd cycle ONLY:** Measurement of blood pressure and heart rate; Blood sampling(s) will allow the measurement (local laboratories) of the whole set of “Safety Laboratory Tests” i.e.: hematocrit, hemoglobin, red blood cells, platelets, white blood cells, differential white blood cells count, sodium, potassium, serum creatinine, serum albumin, blood urea nitrogen, total bilirubin, ALT, AST.

Laboratory results and ECG reading MUST be made available before the Treatment Box for the next treatment cycles is dispensed.

As per discontinuation criteria (see [Section 6.3.2](#)), **no IMP will be dispensed** in the case:

- QTcF is either > 500 msec or increases by > 60 msec from screening measurement on two consecutive ECG readings taken 1 hour apart;
- The patient develops LBBB, or atrio-ventricular or heart block;
- The patient develops any significant cardiovascular disease;
- The patient develops renal (calculated CL_{cr} < 60 mL/min) or hepatic (increased ALT/AST > 3 x ULN and increased total bilirubin > 3mg/dL [$>51.3 \mu\text{mol/L}$]) dysfunction as well as hypoalbuminemia;
- Pregnancy occurs (female patient).

After having confirmed the patient has not developed a condition that prevents his/her continuing participation into the study, he/she will be provided with the Treatment Box - Cycle No. 2 or Treatment Box - Cycle No. 3 (as appropriate) matching his/her randomization number, together with the Diary Card.

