14.3. APPENDIX 14.3 – STUDY FLOW CHART

		100 days														
		VISIT	SCREENING (one or more visits)		Pre-dose visit (2nd cycle)	Pre-dose visit (3rd cycle)	FU visit 3months	FU visit 6months	FU visit 12months							
		Week	From enrolment	- 3 to 0	1-2	4	5-6	8	9-10	11 12	13±1	24 25	26±2	50 51	52±2	
1st INSULIN ADMINISTRATION	ENROLLMENT (consent signed)	ASSESSMENTS	Past medical history and disease-specific information	BP/HR, Weight, Height Safety lab test (hematology & biochemistry) 12 lead ECG Pregnancy	RANDOMIZATION – STUDY DAY 0 [1 st cycle IMP dispensed]	Treatment cycle No.1 (start on Study Day 1)	BP/HR Safety lab test (hematology & biochemistry) 12 lead ECG (repeat 1 hour apart if QTcF is EITHER > 500 msec OR has increased by > 60 msec from screening value) Pregnancy	Treatment cycle No. 2	serum creatinine and albumin, total bilirubin, ALT/AST, 12 lead ECG (repeat 1 hour apart if QTcF is EITHER > 500 msec OR has increased by > 60 msec from screening value) Pregnancy	Treatment cycle No. 3	Pre-visit phone call	Insulin (IU/kg/day) Severe hypoglycaemia HbA1c, Auto-Ab and miR-375	Pre-visit phone call	Insulin (IU/kg/day) Severe hypoglycaemia HbA1c, Auto-Ab and miR-375	Pre-visit phone call	Insulin (IU/kg/day) Severe hypoglycaemia HbA1c, Auto-Ab and miR-375
			Auto-Ab to confirm diagnosis	Baseline Insulin (IU/kg/day) Baseline \$ HbA1c, Auto-Ab and miR-375			MMTT C-peptide glucose glucagon		MMTT C-peptide glucose glucagon			MMTT C-peptide glucose glucagon				
				Baseline MMTT# C-peptide, glucose, glucagon			2 nd cycle IMP dispensed if no contraindication has arisen (see discontinuation criteria below*)		3 rd cycle IMP dispensed if no contraindication has arisen (see discontinuation criteria below*)			BP/HR Safety lab test (hematology & biochemistry)				
			T-cell response ex vivo §								T-cell response ex vivo §		T-cell response ex vivo §		T-cell response ex vivo §	

Assay of green entries will be done at a centralized laboratory. Auto-Antibodies (Auto-Ab) include anti-GAD; IAA; IA-2 antibody; ZnT8. [\$ Baseline Auto-Ab test will not be repeated if test to confirm diagnosis is done within the -3 to 0 week timeframe].

= Baseline MMTT should be planned to ensure the sample is sent to the centralized laboratory and C-peptide result is available (consider 5 working days) in time for randomization.

§ = T-cell to be collected at selected sites only.

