14.4.2. Mixed Meal Tolerance Test

The MMTT will be performed after an overnight fast, according to [Greenbaum \(2008\)](#) at baseline (within 1 week prior of randomization) and at each follow-up visit on weeks 13_±1, 26_±2 and 52_±2. Screening MMTT should not be performed within one week of resolution of a diabetic ketoacidosis event, defined as the presence of hyperglycemia (blood glucose >200 mg/dL); pH <7.3 or HCO₃ <15; ketones positive in the serum or urine.

Prior to the test, patients will withhold long-acting insulin on the morning of the test. Rapid-acting and short-acting insulin will be allowed up to 6hrs and 2 hrs, respectively, before the test. Test will be re-scheduled if the patient has a capillary glucose value of >200mg/dL or <70mg/dL.

The test will be initiated before 10 a.m. After 2 pre-meal basal samples have been drawn between -20 to 0 min (basal 1 and basal 2), patients will be given 6mL/kg of Boost[®] High Protein Nutritional Drink (Nestlé Nutrition) up to a maximum of 360mL, to be drunk within 5 min. Post-meal samples will be drawn at 15_±5, 30_±5, 60_±10, 90_±10, 120_±15, 180_±15 min after the meal.

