#### 4.1.4. DESCRIPTION OF THE STUDY FLOW

Each patient will be involved in the study for a screening period up to 100 days followed by a post-randomization period up to 52±2 weeks.

The study consists of the following periods:

- 1) **Screening period**, including 2 or more visits during a period up to 100 days; this includes the time required to confirm the diagnosis.

Potential study patients with a recent clinical diagnosis of T1D will be identified from those referring to the site for diagnosis confirmation (auto-antibody testing) and/or disease management.

Enrolment is defined as signature of the Informed Consent Form (ICF) for study participation. From enrolment, patients will be admitted to an intensive diabetes management, according to current ADA recommendation. Patients will self-monitor glucose levels at least 4 times a day and will take insulin as prescribed by the Investigator throughout the study participation. To ensure standardized glycemic control in the treatment groups, the Investigator will provide guidance for insulin regimen adjustment.

Compliance with inclusion/exclusion criteria will be finally verified vs demographic, laboratory test results and clinical information (baseline assessments to be completed within 3 weeks before randomization).

- 2) **Randomization**: Patients fulfilling **all** the inclusion criteria and **none** of the exclusion criteria will be randomized, randomization to occur within 100 days from the 1st insulin administration. Randomization is defined as **Study Day 0** with reference to day when IMP administration is started, which is defined as **Study Day 1**.
- 3) **Treatment period**, including 3 treatment cycles of 2 weeks each with 2 weeks' interval between cycles and 2 corresponding pre-dose assessment visits.

Assessments to be done before the 1st dose in the 1st treatment cycle are part of the screening evaluation. Thereafter, patients will refer to the site within 1 week ("pre-dose visits") before the expected date when the 2nd or 3rd treatment cycle is due to start to confirm no condition that prevents their continuing participation into the study has arisen. The amount of IMP for each treatment cycle will be dispensed only after compliance with criteria for drug administration has been confirmed.

- 4) **Follow-up period**: 3 follow-up visits scheduled at weeks 13±1 (month 3), 26±2 (month 6) and 52±2 (month 12).

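### The only pregnancy test before the first dose may be up to 21 days old at randomization (22 at first dose), while cycles 2 and 3 require one within a week of the expected start

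*Protocol*

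**What the plan says.** Protocol 7.1.2 lists the pregnancy test (dipstick or blood, where appropriate) among the assessments due "within 3 weeks before randomization (baseline measurements", and says that screening "may be performed in one or more visits". The synopsis gives the same 3-week frame for assessments that "will be also performed during the screening period". The flow chart in Appendix 14.3 puts the test in the column for weeks -3 to 0, in the entry "BP/HR, Weight, Height Safety lab test (hematology & biochemistry) 12 lead ECG Pregnancy". SAP 4.1.4 agrees: "baseline assessments to be completed within 3 weeks before randomization".

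For cycle 1, Protocol 7.2.1 states "Assessment to be done before the 1st dose are part of screening evaluation" and has the cycle 1 box handed over on Day 0. No new test is listed.

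For the later cycles, Protocol 7.2.2 states "Patient will refer to the site within 1 week before the expected date when the 2nd or 3rd treatment cycle is due to start". A pregnancy test is part of that visit, and no drug is dispensed if the patient is pregnant.

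SAP 16.6 lists the same three tests: screening, pre-dose cycle 2 and pre-dose cycle 3. Its only country-specific addition is a Belgian test at month 3, after dosing has ended.

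**The concern.** A negative pregnancy test says nothing about conception after the sample was taken, so its age at dispensing matters. Of the three dispensings, the first may rest on the oldest result, and it is also the first time this drug is given to women: Protocol 2.4 reports that all 119 earlier trial subjects, 93 of them exposed, were male.

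A pregnancy missed at the start could be exposed to the whole 14-day first cycle at 400 mg twice daily, because the next planned test falls after that cycle ends. The rat study in Protocol 2.2 found nothing attributable to the drug in females up to 200 mg/kg, but it covers fertility and early development to implantation. Section 2.2 summarises no study of later embryo-fetal development, although other documents may hold such data.

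**Working it through.** The documents give no figure of their own to reproduce, so the check is a day count followed by a rough sizing.

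**Age of the test.** Randomization is Day 0 and first dose is Day 1 (Protocol 7.1.3; SAP 7.1).
- Earliest permitted baseline test: 3 × 7 = 21 days before Day 0, that is Day -21.
- Age at randomization: 21 days. Age at first dose: 21 + 1 = 22 days.
- Cycle 2 is due on Day 29 (14 days on, 14 off), so its test falls on Days 22 to 28, at most 7 days before the expected start. The same limit holds for cycle 3.

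All these limits lengthen if a start slips. The protocol sets no separate limit on the gap from Day 0 to Day 1.

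**Where the true age may be lower.** Appendix 14.4.2 has the mixed meal test done "at baseline (within 1 week prior of randomization) and at each follow-up visit". A pregnancy test taken at that visit would be at most 7 days old at randomization. Section 7.1.2, however, lists that meal test under the 3-week window too, and nothing ties the pregnancy test to the same visit.

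**Whether another test closes the gap.** The final eligibility check in Protocol 7.1.3 reviews existing results and requires no new test. For the extra German visit on Days 3 to 5 of cycle 1, the SAP describes vital signs, ECG and laboratory tests (16.4.5, 16.5, 16.7), but no pregnancy test.

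**Rough size.** The documents give neither the number of women nor a pregnancy rate. Assume 24 to 36 women among the 72 patients and 1% to 10% pregnancies per woman-year on contraception. Extra conceptions = women × rate × extra days / 365, where extra days are those beyond a 7-day limit.
- Every woman tested on Day -21: 21 − 7 = 14 extra days.
- Test days spread evenly over the 21 days: mean excess = (14 × 14 / 2) / 21 = 4.67 days.

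| Scenario | Low | High |
|---|---|---|
| All at Day -21, both arms | 24 × 0.01 × 14/365 = 0.009 | 36 × 0.10 × 14/365 = 0.138 |
| Evenly spread, both arms | 24 × 0.01 × 4.67/365 = 0.003 | 36 × 0.10 × 4.67/365 = 0.046 |
| All at Day -21, ladarixin arm (× 2/3) | 0.006 | 0.092 |
| Evenly spread, ladarixin arm (× 2/3) | 0.002 | 0.031 |

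The factor 2/3 is the 2:1 allocation; only women on ladarixin can be exposed.

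**What a later test buys.** Assume a test turns positive 10 to 14 days after conception. The span of conceptions that cannot be seen at first dose is then:
- as planned: 22 + (10 to 14) = up to 32 to 36 days;
- with a 7-day limit before randomization: 8 + (10 to 14) = 18 to 22 days;
- with a Day 0 test: 1 + (10 to 14) = 11 to 15 days.

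The window shrinks but does not close.

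**The case against.** The strongest reply is that this is a choice, not an error. No passage contradicts a 3-week baseline window, and the same window covers the ECG, safety laboratory tests and vital signs. The 1-week visits in 7.2.2 are on-treatment checks tied to stopping rules, so they are not a standard that the baseline window breaches. Eligibility is verified finally before randomization, and exclusion criterion 14 rules out pregnant women and those unwilling to use effective contraception. In practice many women may be tested at the meal test visit, inside a week.

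Much of this stands. A reader might infer that women will routinely start drug on a three-week-old test, or that the protocol breaks its own rule. The documents support neither: 22 days is a ceiling, how often a test would exceed 7 days is unknown, and the 1-week rule was written for cycles 2 and 3 only. A reader might also infer a material risk of exposed pregnancies, but the expected count is well below one and rests on assumed inputs.

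What does not stand is that the existing safeguards make a newer test redundant. The final verification can rely on the old result. The contraception criterion concerns willingness and names an end point (2 months after dosing) but no start. Unlike most baseline findings, pregnancy is both an absolute exclusion and a reason to stop drug.

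**Conclusion.** The point holds as a minor, inexpensive tightening for participant safety. The plan permits a pregnancy test up to 21 days old at randomization and 22 days old at first dose, against 7 days before the expected start of cycles 2 and 3. The day count follows directly from the documents, taking first dose as the day after randomization.

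The clinical size cannot be derived from them. On the assumed numbers of women and pregnancy rates, the extra conceptions in women given ladarixin are at most about 0.006 to 0.092, or about 0.002 to 0.031 with evenly spread test days. No objective, endpoint or analysis is affected.

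**What to change.** Keep the screening test. In Protocol 7.1.2, 7.2.1, Appendix 14.3 and the synopsis, require a negative pregnancy test (dipstick allowed, where appropriate) on Day 0 before the randomization number is assigned, or within the 7 days before randomization with the result available at that point. Repeat the dipstick only if the screening test is older than that.

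The test should come before randomization, not merely before the box is dispensed. A positive result after number assignment would leave a randomized, untreated patient who cannot be replaced (Protocol 7.4.2) and who falls outside the ITT set, which requires receipt of drug (Protocol 9.3; SAP 6.4).

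The cost is at most one extra dipstick per woman of childbearing potential, so no more than 24 to 36 on the assumption above. No extra visit is needed, because the patient already receives the box on Day 0. The SAP needs no new analysis: its baseline (7.2) is already the last measurement before drug. A very recent conception, or one during cycle 1, would still be missed until the Day 22 to 28 test at the earliest.

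In the same edit, the references to 7.1.1 in 7.2.1 and 7.2.2 can be corrected to 7.1.2. That slip is clerical and carries no weight here.

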7.2.2. Pre-dose assessment - 2nd and 3rd treatment cycle

Patient will refer to the site within 1 week before the expected date when the 2nd or 3rd treatment cycle is due to start. The following will be evaluated:

- General clinical evaluation to ensure patients has not developed concurrent clinical conditions, including pregnancy in female participants, which in the opinion of the Investigator may pose a safety risk for continuing participation in the study
- Blood sampling(s) for measurement (local laboratories), of serum creatinine, serum albumin, total bilirubin, ALT, AST. Renal and hepatic function will be evaluated as per details in [Section 7.1.1](#) above.
- 12 lead ECG performed using local equipment that allows automatic calculation of the QTcF. If the QTcF is EITHER > 500 msec OR has increased by > 60 msec from baseline value, a second reading will be obtained 1 hour later.
- Pregnancy test (urine dipstick or blood sample), if appropriate.
- **On pre-dose 2nd cycle ONLY:** Measurement of blood pressure and heart rate; Blood sampling(s) will allow the measurement (local laboratories) of the whole set of “Safety Laboratory Tests” i.e.: hematocrit, hemoglobin, red blood cells, platelets, white blood cells, differential white blood cells count, sodium, potassium, serum creatinine, serum albumin, blood urea nitrogen, total bilirubin, ALT, AST.

Laboratory results and ECG reading MUST be made available before the Treatment Box for the next treatment cycles is dispensed.

As per discontinuation criteria (see [Section 6.3.2](#)), **no IMP will be dispensed** in the case:

- QTcF is either > 500 msec or increases by > 60 msec from screening measurement on two consecutive ECG readings taken 1 hour apart;
- The patient develops LBBB, or atrio-ventricular or heart block;
- The patient develops any significant cardiovascular disease;
- The patient develops renal (calculated CL_{cr} < 60 mL/min) or hepatic (increased ALT/AST > 3 x ULN and increased total bilirubin > 3mg/dL [$>51.3 \mu\text{mol/L}$]) dysfunction as well as hypoalbuminemia;
- Pregnancy occurs (female patient).

After having confirmed the patient has not developed a condition that prevents his/her continuing participation into the study, he/she will be provided with the Treatment Box - Cycle No. 2 or Treatment Box - Cycle No. 3 (as appropriate) matching his/her randomization number, together with the Diary Card.

Before box delivery, the removable label on the Treatment Box (see [Section 6.4](#)) will be detached and attached to the relevant CRF page.

It is the responsibility of the Investigator (or designee) to check the Diary Card completed for the previous administration period to ensure correct intake of the IMP. The Investigator will remind, and make sure patient still fully understands any appropriate treatment related information.

